POB/ /
Berlaku mulai:

15 Mei 2015

http://www.pjnhk.go.id/

Study Protocol

Hal 1 dari 6

LAMPIRAN 3 FL/03-010/01.0

Study Protocol Summary

Title

Low Dose Continuous Furosemide Effect on Cardiac Surgery Patients With Kidney Dysfunction

Main Researcher

dr. [name], SpAn., M.Kes., KAKV

RS Jantung dan Pembuluh Darah Harapan Kita, Jakarta

Sponsor

none

Aims

- to Analyze trends in estimated glomerular filtration rate parameters from administration of low-dose furosemide continuous infusion in patients with mild-moderate renal dysfunction undergoing cardiac surgery.
- 2. 2. To analyze the need for a therapeutic dose of intravenous diuretic after low-dose continuous furosemide in patients with mild to moderate renal dysfunction undergoing cardiac surgery.
- 3. To analyze the need to use renal replacement therapy as a marker of worsening renal function leading to acute renal failure after continuous administration of low-dose furosemide in patients with renal dysfunction undergoing cardiac surgery.

Ethical Issue(s) of the Protocol

- 1. Administration of fluids or drugs to patients that can affect patient outcomes
- 2. Taking blood samples from patients for laboratory examination
- 3. Evaluating the effects of drug administration
- 4. Patient condition follow up in study period
- 5. Inconvenience of patient or family for additional information needed in research involvement

POB/ /
Berlaku mulai:

15 Mei 2015

Hal 2 dari 6

LAMPIRAN 3 FL/03-010/01.0

http://www.pjnhk.go.id/

Study Protocol

Study Design

Clinical Study: double blinded randomized controlled study

Anticipated Outcome

Perioperative administration of low dose continuous furosemide infusion can gives protective effect in cardiac surgery patients with mild to moderate kidney, Measured by the improvement of post operative eGFR

Inclusion and exclusion criteria

Inclusion criteria:

- 1) 18-65 years old
- 2) Undergo elective heart surgery, types of surgery: coronary bypass (coronary artery bypass graft/CABG), single heart valve replacement surgery, one or two heart valve repair surgery, coronary bypass surgery with single heart valve repair/replacement.
- 3) Using cardiopulmonary bypass machine in surgical procedures
- 4) Patients with ejection fraction >40%
- 5) Patients with mild to moderate impaired renal function (eGFR 30-89 mL/min/1.73 m2 and have never had renal replacement therapy

Exclusion criteria:

- 1) Heart disease patients with ejection fraction < 40%

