Ethical clearance for the study was approved by Institutional Review Board of National Cardiovascular Center Harapan Kita. Patients eligible for the study was recruited and written informed consent was obtained after clear explanation of the study. Allocation of furosemide and control group was done using simple computer randomization by staff who was not involved in the study. Furosemide infusion and normal saline was prepared by independent pharmacist blinded to the study. Furosemide solution was prepared to contain 40 mg of furosemide diluted with normal saline to a total volume of 40 cc (1 mg / 1 cc) and control solution was prepared to contain only 40 cc of normal saline. Both solution was packaged in 50-cc syringe and prepared in similar fashion. The solution was administered after induction of anesthesia with rate of 2 cc

Study Protocol

POB/ /
Berlaku mulai:

15 Mei 2015

Hal **4** dari **6**

LAMPIRAN 3 FL/03-010/01.0

http://www.pjnhk.go.id/

per hour for 12 hours.

Metode Analisa*

The data obtained will be analyzed using the SPSS software program. Basic characteristic data will be displayed according to the specified variable type. Numerical variables with normal distribution will be displayed in the form of mean ± standard deviation or median (minimum-maximum) if the distribution is not normal. Categorical variables will be displayed as a percentage (amount). Data from the two groups were analyzed using x2 analysis (chi square) or Fisher's exact test, respectively. The level of statistical significance refers to the P value <0.05

Evaluation Criteria (Response/Outcome)

changes in glomerular filtration rate parameters after intervention in subjects will be evaluated, the need/indication for therapeutic diuretic therapy, and use of renal replacement therapy, length of stay in the ICU and incidence of mortality will be analyzed.

Safety Parameters Criteria (Toxicity)

Renal Function pre and post treatment

Blood gas analysis

Blood electrolyte

POB/ /
Berlaku mulai:

15 Mei 2015

Study Protocol Hal 5 dari 6

LAMPIRAN 3 FL/03-010/01.0

http://www.pjnhk.go.id/

Abstract

[figure not shown]
Background:

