The study design was a double-blind randomized controlled trial. Subjects will be randomly divided into 2 groups; the furosemide group (n=43) and the control group (n=44). This study started since May 28, 2021; after obtaining an ethical clearance from the hospital ethics committee. Inclusion criteria included patients aged 18-65 years with left heart ejection fraction >40%, mild to moderate renal dysfunction category (eGFR 30-89 mL/min/1.73 m2) who underwent elective cardiac surgery; such as coronary artery bypass graft (CABG), replacement of one heart valve, repair of one or two heart valves, and using cardiopulmonary bypass machine. Exclusion criteria included heart disease patients with stage 4-5 chronic renal failure, on renal replacement therapy, cardiac ejection fraction <40%, emergency or repeat surgery, complex heart disease, congenital heart disease, aortic vascular surgery, massive bleeding, sepsis, and currently participating in other research. Continuous furosemide (2 mg/hour) or 0.9% NaCl (2 mL/hour) was given after the induction of anesthesia and continued until 12 hours of administration. After drug administration was completed (12 hours) the first blood sample was obtained to check blood urea nitrogen concentration, urea, creatinine serum and estimated glomerular filtration rate. Sampling was repeated again at the 24th hour, 48th hour and 120th hour since the drug was started. A decrease in GFR > 20% of the preoperative value is considered a decrease in renal function, and an increase of >20% of third sample value in the fourth sample is considered an improvement of renal function. Deterioration of renal function to severe renal dysfunction or requiring renal replacement therapy is considered an event of acute renal failure.

Keywords: Furosemide, Glomerulus Filtration Rate, Renal Dysfunction, Cardiac Surgery

Researcher,

dr. [name], SpAn, M.Kes, KAKV

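### The eGFR improvement rule has no exception for renal replacement therapy and no result for death before 120 h, so within that endpoint it favours the arm with more failures

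*Combined protocol and SAP*

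**What the plan says.** The outcome definitions are in the Methods part of the Abstract in the combined protocol and SAP. The first sample is taken when the 12-hour infusion ends. After that, "Sampling was repeated again at the 24th hour, 48th hour and 120th hour since the drug was started", so the third sample is at 48 h and the fourth at 120 h.

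Three classifications follow:

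- Decrease: "A decrease in GFR > 20% of the preoperative value is considered a decrease in renal function".
- Improvement: "an increase of >20% of third sample value in the fourth sample is considered an improvement of renal function".
- Acute renal failure: "Deterioration of renal function to severe renal dysfunction or requiring renal replacement therapy is considered an event of acute renal failure".

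No section ranks these categories or makes them mutually exclusive. No section says how RRT, death or a missing sample enters the eGFR classification.

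The Anticipated Outcome section describes the expected benefit as "Measured by the improvement of post operative eGFR". The Evaluation Criteria section lists GFR change and the need for diuretics, "and use of renal replacement therapy, length of stay in the ICU and incidence of mortality will be analyzed". The third aim is "To analyze the need to use renal replacement therapy as a marker of worsening renal function leading to acute renal failure". The analysis section (Metode Analisa) names only chi-square and Fisher's exact tests for comparing the groups.

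**The concern.** The improvement rule compares two eGFR values and asks nothing about what happened between them. eGFR is calculated from serum creatinine, which RRT removes. A value taken after RRT has started can therefore be higher than the one before it although the kidney has not recovered. If RRT starts between the third and fourth samples, the rule can record a success for a patient whom the next sentence of the same text classes as a failure.

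A patient who dies before 120 h has no fourth sample. The rule gives no result, so by default that patient leaves the improvement comparison.

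Both routes raise the improvement rate of the arm in which they occur more often, which is the arm with more failures. Improvement in postoperative eGFR is how the protocol describes the expected benefit, so the distortion falls on an endpoint tied to that claim.

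**Working it through.** The plan gives no RRT rate, death rate, expected improvement rate or power calculation, so there is no figure of its own to reproduce. The check applies the written rules to assumed patients and then asks how far a few such patients could move the comparison.

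**Inputs from the documents.** Group sizes 43 (furosemide) and 44 (control); improved if eGFR at 120 h > 1.2 × eGFR at 48 h; decreased if eGFR < 0.8 × the preoperative value; RRT is an acute renal failure event.

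**1. One patient under all three rules (assumed values).** Preoperative eGFR 60, 48 h value 20, RRT started, 120 h value 26.

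- Change from 48 h: 26/20 − 1 = +30%, so improved.
- Change from preoperative: 26/60 − 1 = −57%, so decreased.
- RRT was required, so acute renal failure.

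All three labels apply to the same patient.

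**2. How small a creatinine fall is enough.** Assume eGFR varies as creatinine to the power −k. The fall needed for a 20% rise in eGFR is 1 − 1.2^(−1/k).

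- k = 1.0: 16.7%
- k = 1.1: 15.3%
- k = 1.2: 14.1%

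The rule cannot tell whether the kidney or RRT produced that fall.

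**3. Effect of one patient.** A patient wrongly scored as improved adds 1/43 = 2.33 points (furosemide) or 1/44 = 2.27 points (control). Dropping a patient who did not improve changes b/n to b/(n − 1), a gain of b/[n(n − 1)], where b is the number improved. With b = 9 and n = 44 this is 9/(44 × 43) = 0.48 points. The gain cannot exceed 1/n.

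**4. Effect of several patients (assumed counts).** Take 9/43 = 20.9% and 9/44 = 20.5% genuine improvers, and place all affected patients in the control arm.

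| Affected control patients | RRT scored as improved | Deaths dropped | Counted as not improved |
|---|---|---|---|
| 1 | 10/44 = 22.7% | 9/43 = 20.9% | 9/44 = 20.5% |
| 2 | 11/44 = 25.0% | 9/42 = 21.4% | 20.5% |
| 3 | 12/44 = 27.3% | 9/41 = 22.0% | 20.5% |
| 4 | 13/44 = 29.5% | 9/40 = 22.5% | 20.5% |

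With four RRT patients scored as improved, the apparent advantage of the control arm is 29.5 − 20.9 = 8.6 points (Fisher p = 0.46). With base rates near 10% and 30% it is 18.2 − 9.3 = 8.9 points (p = 0.35) and 38.6 − 30.2 = 8.4 points (p = 0.50).

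**5. Does another section close the gap?** The withdrawal criteria name neither RRT nor death. They cover haemodynamic instability, shock, long bypass and similar events, but do not say how withdrawn patients enter the analysis. The analysis section has no rule for missing samples.

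**The case against.** The strongest reply is that these patients remain visible. RRT counts as acute renal failure in the sentence after the improvement rule, RRT and mortality are listed outcomes, and the need for RRT is an aim. This stands. A reader might infer that kidney failures are turned into successes, or vanish, in the trial as a whole. The documents do not support that, and a death is not necessarily a kidney failure.

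The size is also uncertain. A reader might assume a split such as 1 RRT case in 43 against 3 in 44 and report a false gap of 6.8 − 2.3 = 4.5 points. The documents give no source for any split. That figure also needs every case to start RRT after the 48 h sample and then rise by more than 20%; RRT begun earlier may already have raised the reference value. Patients are elective, aged 18 to 65, with ejection fraction above 40%, and some of the sickest may be withdrawn. Few may be affected, and even four in one arm would not by themselves give a significant difference.

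The link to the benefit claim is partly inferred. The Anticipated Outcome section does not cite the 48 h to 120 h rule, no primary endpoint is named, and no test of mean eGFR is planned. Distortion of a comparison of means is therefore not a finding here.

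Finally, a reader might see a contradiction in any patient who is both decreased and improved. The two rules use different reference values, so both labels can describe a dip followed by partial recovery. With assumed values of 60 preoperatively, 30 at 48 h and 45 at 120 h, eGFR has risen 50% from 48 h and is 25% below preoperative. That needs no correction.

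Separate reporting of RRT and death does not repair the improvement endpoint. The same patient can still be a success in one table and a failure in another, and the choice is left open until the data are seen.

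**Conclusion.** The point holds within the improvement/eGFR endpoint. Followed exactly, the rule can give a wrong result for a patient who starts RRT between 48 h and 120 h, and it gives none for a patient who dies before 120 h. Both effects favour the arm with more failures.

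The size is up to about 2.3 points per affected patient, and usually less for a dropped death. The total cannot be derived: it is zero if no patient is affected, and may be a few points otherwise. The direction rests on RRT lowering creatinine, which is general knowledge and not a statement in the documents, and on patients without a fourth sample being left out by default. All patient values and counts in the check are assumptions. The change should be made because the gap is definite and cheap to close, not because a large bias has been shown.

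**What to change.** Add to the outcome definitions in the Methods part of the Abstract, before the groups are compared:

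> A patient who starts RRT or dies before the fourth sample is counted as not improved and stays in the denominator. eGFR values measured after RRT starts are not used as measures of kidney function.

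Add a sensitivity analysis that excludes these patients. No further condition is needed: not a requirement that eGFR at 120 h be near the preoperative value, nor scoring deaths as a renal decrease, nor a ranked analysis.

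The cost is two sentences and one extra table. Treatment and sampling do not change, and RRT and mortality are already outcomes, although the timing of each relative to the fourth sample must be available. The improvement rate becomes slightly lower, and a patient who starts RRT and does recover by 120 h is also counted as not improved.

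### Does the wider acute renal failure definition in the Abstract leave Aim 3 without a settled outcome?

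*Combined protocol and SAP*

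**What the plan says.** Three places bear on this.

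- **Aims, item 3:** "To analyze the need to use renal replacement therapy as a marker of worsening renal function leading to acute renal failure". The quantity to be analysed is the need for RRT, and it is described as a marker.
- **Evaluation Criteria (Response/Outcome):** after change in GFR and the need for diuretic treatment, the list continues: "use of renal replacement therapy, length of stay in the ICU and incidence of mortality will be analyzed". Acute renal failure is not in the list.
- **Abstract, Methods:** "Deterioration of renal function to severe renal dysfunction or requiring renal replacement therapy is considered an event of acute renal failure". This follows two other classification rules. One is for worsening: "A decrease in GFR > 20% of the preoperative value is considered a decrease in renal function". The other is for recovery: "an increase of >20% of third sample value in the fourth sample is considered an improvement of renal function".

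The sampling schedule is in the same paragraph. The first sample is taken at the end of the 12-hour infusion, and then: "Sampling was repeated again at the 24th hour, 48th hour and 120th hour since the drug was started".

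**The concern.** The Abstract's event is wider than RRT use, because it adds every patient who reaches severe renal dysfunction without RRT. It is phrased as a counting rule, yet no aim or outcome list mentions it and no analysis is attached to it. A reader could therefore ask whether Aim 3 is to be answered by RRT alone or by the wider event.

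The wider event is also incompletely specified. It prints no eGFR value for severe, and it does not say which of the four post-drug samples decides, although the recovery rule just before it names its two samples. A patient who is in the severe range at 24 h and out of it by 120 h is an event under one reading and not under another.

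With 43 and 44 patients and possibly few events, one patient's classification could decide significance. If the choice of count were made after results by arm were known, the reported P value could not be taken at face value.

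**Working it through.** The plan gives no event rate, effect size or power for this outcome, so there is no stated figure to reproduce. The check is mainly a reading of the text, with one calculation to size the stake.

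**1. Which count is analysed?** The Evaluation Criteria say RRT use will be analysed, and Aim 3 sets out to analyse the need for RRT. The aim and the outcome list agree.

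**2. Are there two definitions of acute renal failure?** No. Aim 3 treats RRT as a marker of worsening on the way to acute renal failure and does not equate the two. Only the Abstract defines the event. The counts are nested:

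events (Abstract) = patients with RRT + patients in the severe range without RRT

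The RRT count is therefore unaffected by how the second term is settled.

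**3. What is open in the second term?**

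- *Cut-off.* Mild to moderate is labelled as eGFR 30-89 in the inclusion criteria, and stage 4-5 disease is excluded. Severe as below 30 is an inference, but the documents leave little room for another value.
- *Minimum fall.* The event sentence makes no reference to the >20% rule, so none is required as written.
- *Deciding sample.* This is not stated. For a per-sample severe rate q, the proportion of patients severe in at least one of four samples lies between q (the same patients each time) and 4q (different patients each time). At an assumed q of 5% the range is 5% to 20%, or 1 − 0.95⁴ = 18.5% if the samples were independent. The 5% is an illustration; the documents give no rate.

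**4. How sensitive is the test?** Inputs: 43 furosemide and 44 control patients (Abstract, Methods), Fisher's exact test and P<0.05 (Metode Analisa); two-sided testing is assumed. With m events, all in control, the two-sided P value is the sum of the two extreme splits:

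P = [C(44,m) + C(43,m)] / C(87,m)

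- m = 5: (1,086,008 + 962,598) / 36,949,857 = 0.055
- m = 6: (7,059,052 + 6,096,454) / 504,981,379 = 0.026

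Other splits (furosemide v control): 1 v 6 gives 0.110, 1 v 7 gives 0.058, 1 v 8 gives 0.030 and 2 v 8 gives 0.089. One patient moved can cross 0.05.

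The plan allows chi-square or Fisher's and states no rule for choosing. Uncorrected chi-square gives 0.043 at 0 v 4 and 0.023 at 0 v 5, so the threshold of six control events belongs to Fisher's test and not to the plan as such.

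**5. What does step 4 show?** The same arithmetic applies to mortality, or to any sparse yes/no outcome at 43 v 44, however well it is defined. It measures the fragility of small counts. It does not measure the distance between RRT use and the wider event, which would need an RRT rate and an eGFR distribution.

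**The case for a change.** The strongest case for a change is that the Abstract's sentence is written as a rule for counting and cannot be applied as it stands. A reader cannot tell whether it supplements RRT use, replaces it for Aim 3, or is only descriptive. Any sample and the last sample alone would give different totals, and near the thresholds above that could alter a conclusion. The remedy would cost only a few clauses and no new data. The Abstract also reports that "This study started since May 28, 2021", so any clarification would have to be dated against access to results by arm.

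Part of this stands. The event has no stated analysis and no deciding sample, while the recovery rule shows that the authors could name samples when they chose to. Replacement of RRT use is not a fair reading, however, because the outcome list names RRT and omits the event. The possible flip in significance attaches to an outcome that the plan does not say it will test.

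**Conclusion.** The concern does not call for a change. RRT use is the analysed outcome for Aim 3, the aim and the outcome list agree on it, and the Abstract's event includes RRT without contradicting either. Following the plan as written, with RRT use compared by arm and eGFR change evaluated separately, gives no wrong result.

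What survives is missing detail in an unlisted event: its role, its printed cut-off and its deciding sample. An analyst who chose to report it would sensibly take severe as below the 30-89 band, say which samples were used, and show the eGFR part and RRT use separately by arm. Writing that down would be tidier, but it offers no better method than the plan already has.

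The size of the gap is unknown. The Fisher values are correct, but they illustrate small-sample fragility only and rest on assumed two-sided testing and on Fisher's being the test used. The conclusion rests on reading the Evaluation Criteria as the list of outcomes to be analysed. If the wider event were later presented as the answer to Aim 3 in place of RRT use, that would be a departure from the plan and should be reported as one.
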